13.6 SUBJECT POPULATION FOR ANALYSIS

All subjects who are randomized will be analyzed according to the Intent-to-Treat study design.

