3.0 PROTOCOL SUMMARY

Title	Combining Pregabalin (LYRICA®) with Lofexidine (LUCEMYRA™): Can it Increase the Success of Transition to Naltrexone?						
Short Title	Pregabalin and Lofexidine for opioid withdrawal						
Protocol Version	7.0						
Phase	Phase 2						
Methodology	Double-blind placebo-controlled parallel group clinical trial						
Study Duration	24 months						
Study Centers (3)	 University of Pennsylvania Center for Studies of Addiction in Philadelphia Pennsylvania Columbia University in New York City, New York Mountain Manor in Baltimore, Maryland 						
Objective (Primary)	To investigate whether pregabalin-Lyrica® (PGB) combined with Lofexidine-Lucemyra® (LFX) can reduce opioid withdrawal-related subjective effects						
Objective (Secondary)	To investigate, if the PGB/LFX combination can increase the proportion of patients with an opioid use disorder (OUD) who complete detoxification and transition to antagonist treatment with extended- release injectable naltrexone VIVITROL® (XR-NTX)						
Number of Subjects	90 subjects. 60 randomized to PGB/LFX; 30 to PGB-PLA/LFX						
Inclusion Criteria	 Male and/or female subjects ≥ 18 years of age Meet DSM-5 criteria for an Opioid Use Disorder with physiologic features. Have 2 or more of the 11 DSM 5 criteria for opioid disorder including tolerance and withdrawal features in the last 12 months Interested in opioid antagonist treatment Have used opioids in 20 of the past 30 days Have a stable address in the local area; not planning to move; have documents for ID check Absence of medical or psychiatric conditions that are likely to interfere with study participation Have a 12 lead ECG demonstrating a QTc ≤450 msec and a QRS interval ≤120 msec. The site PI has the final determination for inclusion into the study for ECGs unless there is a question of QT prolongation or other factors (QTc/Fri uses the Fridericia formula (QTc = QT/RR(1/3)). If consultation is needed, the PENN cardiologists and the medical monitor should be contacted. If female, have a negative pregnancy test, and uses adequate contraception if of childbearing potential 						

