9.0 STUDY DESIGN

This study is a phase II, two-part randomized, double-blind placebo-controlled, study to assess the effectiveness of PGB combined with LFX to reduce opioid withdrawal- related subjective effects, and to examine whether a PGB/LFX combination can increase the proportion of opioid use disordered (OUD) subjects who transition to antagonist treatment (XR-NTX).

The study will use three sites, each with inpatient units that provide beds and care from nurses that will be trained in study procedures and dosing requirements. Each site will recruit around 30 randomized subjects, with the Mountain Manor Site and the PENN site possibly recruiting greater than 30 subjects, for a total sample size of 90, using DSM-5 to establish an OUD diagnosis with physiologic features. This trial has 4 distinct phases (see Figure 1 schematic): 1) Outpatient Screening; 2) Inpatient medication induction plus other assessments on Days 1-7; 3) Inpatient XR-NTX administration on Day 8 or 9; and 4) Outpatient Follow-Up (5 days). Total days in study is 15 days plus or minus the time taken to complete the initial outpatient screening assessments. Randomization will occur before inpatient admission.

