9.1 GENERAL DESIGN

9.1.1 Phase 1: Outpatient Pre-Screening (Up to 30 days before hospital admission).

Study inclusion and exclusion criteria will be assessed to make sure the subject meets admission requirements. Those who meet requirements will be given information and details of the study including the timeline, potential risks and benefits, inpatient requirements, confidentiality, and told that participation is voluntary. They will be asked to read the informed consent and encouraged to ask questions, then given a quiz in which they must answer 9 of 10 answers correctly (three retries allowed). Potential subjects will then be asked to sign the informed consent and given a copy.

Once consented, subjects will be screened for up to 30 days to include the following: completion of a locator information form, concomitant medications used in the past 30 days, physical, medical history, complete blood cell count (CBC) with differential and PLT, INR, CMP with magnesium and calcium, urinalysis with reflex microscopy, urine drug screen, a fentanyl urine test, a xylazine urine test, a urine pregnancy test, ECG, creatine kinase test, an eGFR calculation, a Child-Pugh score (liver function), MINI assessment for Opioid Use Disorder with physiologic features (e.g. withdrawal), Insomnia Severity Index (ISI), Clinical Opioid Withdrawal Scale (COWS), Short Opioid Withdrawal Scale (SOWS-G), vital signs (can use manual blood pressure check if considered necessary), Timeline Follow- back (TLFB), Clinical Global Impression Scale (CGI), Hamilton Depression and Anxiety scales (HAM- D, HAM-A), Columbia-Suicide Severity Rating Scale (CSSR-S), an alcohol breathalyzer test, hepatitis B and C tests. Those meeting admission criteria will be asked to report to the inpatient unit on Monday through Friday; randomization will occur at hospital admission. Each collaborating program will enroll around 30 subjects, 20 to receive pregabalin plus lofexidine and 10 to receive placebo pregabalin plus lofexidine. The Pharmacy or designated physician or nurse at each site will receive pre-packaged blinded medications from PENN IDS. All study staff will be blinded.

9.1.2 Phase 2: Inpatient Detoxification (Days 1 thru 7).

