Subjects are admitted to the inpatient unit, randomized to one of the two study medication conditions, and will need to demonstrate withdrawal before starting study medications by having a COWS >/= 6 and a SOWS >/= 4. LFX and PGB dosing will begin at 12:00 on day 1 and a study drug taper will be done from days 5-7. Dose times follow the schedule outlined above and adjustments will be made based on BP changes and/or other AEs. Administration of LFX will be withheld or reduced in cases of dizziness or lightheadedness, clinically significant hypotension and/or the BP changes described above. We will explain to participants the importance for adequate oral hydration during the consenting process and throughout the detox. Similar procedures will be applied to PGB in cases of excessive sedation, dizziness, peripheral edema, or other problematic side effects that appear related that medication.

Dosing schedules are in Tables 2 and 3. Assessments for Day 1 through 7 include:

- 1) ECG is obtained before the 12:00 dose of study medications on Day 1 and before the 08:00 dose of study medications on Day 2-7
- 2) VAS is given before the first dose of study medication at 12:00 on Day 1 and before the 16:00 dose on Day 1. On Day 2-7, the VAS is given before the first dose of study medications at 08:00 and before the 16:00 dose of study medications
- 3) ISI given before the 12:00 dose of study medications on Day 1, and before the 08:00 dose of study medications on Days 2-7
- 4) COWS is given around 12:00 on Day 1 before the first dose of study medication; and around16:00 before the next dose of study medication. If subject is admitted without the requisite withdrawal (COWS >/= 6 and SOWS >/= 4), subsequent COWS and SOWS can be administered before the first dose of study medication until dosing criteria is met.
- 5) SOWS-G is given around 12:00 on Day 1 before the first dose of study medication; and around 16:00 before the next dose of study medication
- 6) POSS is given prior to all doses (08:00, 12:00, 16:00 and 20:00) of study medication
- 7) Sitting and standing blood pressure and pulse are taken prior to each dose of study medication and 1 to 2 hours after dosing, (can use manual blood pressure check if considered necessary)
- 8) Weight taken 1x at screen and Day 15 and recorded on the physical form
- 9) Adverse events/SAEs recorded daily
- 10) Concomitant medication records reviewed and recorded each day
- 11) C-SSRS is given at the end of each study day

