10.0 SUBJECT SELECTION AND DISCONTINUATION

All subjects will be recruited at the site level through newspaper and social media advertising, primary care practices and outpatient facilities, and community referrals. For a more detailed description of recruitment procedures, see section 10.3. Once a potential subject has been identified, a CRA or another study staff person will screen him/her for admission/exclusion criteria. For respondents that appear eligible and are interested in participating, an appointment will be made to come to the research facility and review study procedures, expectations, and other information in more detail. The CRA or another study staff person will explain the study and the potential subject will be asked to read the study enrollment consent, and encouraged to ask questions about anything that is unclear. Subjects still interested in participating will be asked to take a 10-item pre-enrollment guiz and correctly answer 9 of 10 true/false questions about the study to be eligible to continue (three additional tries permitted). A study physician, or other designated clinical staff person will do the medical history and physical. A nurse, physician, medical assistant or other designated personnel will draw blood for screening labs, arrange for an ECG whose results will be reviewed by the PI at the site, and if a problem is found, will transmit a copy to the Study Cardiologist, and/or the study Medical Monitor and/or the Lead Study PI to review before a decision is made as to the next step. If Cardiology is used, each site should have a decision sent back to the site within 24 hours. Upon confirmation that all medical and inclusion and no exclusion criteria are met, a study staff person will randomize the subject and make an appointment for admission to the collaborating inpatient unit.

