10.8 EARLY WITHDRAWAL OF SUBJECTS

All randomized subjects are included in the intent-to-treat analysis. After day 15, or at termination for patients who discontinue the trial prematurely, subjects will be asked to complete the following procedures and assessments: physical exam, vital signs, weight, adverse events; concomitant medications; blood samples for chemistry, CK, CBC with diff and PLT, liver function; urinalysis with reflex microscopy, urine drug toxicology screen; a fentanyl urine test, a xylazine urine test, a pregnancy test for females; and the Clinical Global Impression. ECG will be obtained for early terminators. Subjects will be referred to the most appropriate and available treatment and attempts will be made to obtain these data unless the subject requested they not be contacted or cannot be located.

Subjects will be informed at the consent session that medications could be discontinued if (at the discretion of the principal investigator or site physician): 1) Intolerable side effects occur, or 2) Extreme lab values with a repeat test occur, or that he/she may be discontinued from the study due to

development of psychiatric or medical problems that require a more intensive intervention than provided by the study. Examples are psychiatric symptoms that require inpatient treatment (suicidal ideation, acute psychosis, acute mania); clinical deterioration or a change in status that requires admission to an inpatient medical service; or development of behaviors that compromise safety of the subject or staff. Referrals for care will be made and reasons for subject discontinuation from the study medication and/or clinical trial will be documented on the End of Study Final Evaluation Form.

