13.4 SAFETY OUTCOMES

- 13.4.1 Suicidality. We will compare the groups on presence of active suicidal ideation on the basis of the C-SSRS, which will be administered daily. We define Active Suicidal Ideation to be an endorsement of either Question 4 (active ideation without plan) or 5 (active ideation with plan). If there is sufficient variability in these repeated binary outcomes, we will compare the groups using a mixed effects logistic regression model, similar to the linear mixed effects models described above for the primary outcome; if variability is too low, we will use a (non-mixed-effects) logistic regression model to compare the groups on proportion of participants reporting active ideation at any time in the period
- **13.4.2 Sedation.** The POSS will be administered four times a day on dose days, yielding a set of repeated measures on the POSS score for each participant. We will compare the groups on this score, using linear mixed effects models similar to those described above for the primary outcome.
- **13.4.3** Elevated Creatine Kinase. On day 8 of detoxification, participants will be classified as having elevated creatine kinase if their level is more than three times their screening level. We will compare groups on this response using a logistic regression model with site and group as explanatory variables.
- **13.4.4_Edema**. We will compare groups on the proportion of participants whose study medications were discontinued due to peripheral edema, using a logistic regression model with site and group as the explanatory variables.

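### Section 13.6 applies all-randomised intent-to-treat to safety as well as efficacy, so any never-dosed patients would dilute edema discontinuation and a few other absolute safety rates

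*Combined protocol and SAP*

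**What the plan says.** The statistical plan defines one analysis population, in section 13.6: "All subjects who are randomized will be analyzed according to the Intent-to-Treat study design". Section 10.8 repeats it ("All randomized subjects are included in the intent-to-treat analysis"), as does section 19.2. Section 13.6 follows the methods for efficacy (13.3), safety (13.4) and tolerability (13.5) and does not distinguish between them. No treated-patient or safety set appears anywhere.

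The sections differ on when randomisation happens:

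- Section 9.0: "Randomization will occur before inpatient admission".
- Section 10.0: once eligibility is confirmed, "a study staff person will randomize the subject and make an appointment for admission to the collaborating inpatient unit".
- Section 9.1.1: "randomization will occur at hospital admission". Section 9.1.2 and the protocol summary (3.0) also place it at admission or on Day 1.

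On any of these readings, conditions stand between randomisation and the first dose. Under section 9.1.2 patients "will need to demonstrate withdrawal before starting study medications by having a COWS >/= 6 and a SOWS >/= 4". Sections 7.3.3 and 7.4.4 hold medication for low pulse or blood pressure and for clinically significant QTc prolongation on the pre-dose ECG. At the Columbia site, section 25.0 halts research procedures if the admission COVID test is positive.

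The safety outcome most directly concerned is in 13.4.4: "We will compare groups on the proportion of participants whose study medications were discontinued due to peripheral edema".

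**The concern.** For efficacy, keeping every randomised patient protects the comparison and tends to be conservative. For harms it works the other way. A patient who never took the drug was never at risk of a drug effect, and counting that patient as free of the event lowers the reported risk.

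The combination had not been tested before (10.13.3). Section 7.1.6 makes the absence of extra serious adverse events relative to lofexidine part of the trial's purpose, and 7.1.6 also makes a larger trial depend on the combination appearing safe. A rule that can only pull absolute drug-related risks downward is therefore the wrong default for the safety tables, even if the pull is small.

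**Working it through.** **Is there a figure in the plan to reproduce?** No. The documents state no safety risk, no number never dosed and no confidence limit for a safety risk.

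**Which outcomes are exposed?**

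| Outcome | How a never-dosed patient enters |
|---|---|
| Edema discontinuation (13.4.4) | A known non-event: nothing was started, so nothing was stopped. Diluted. |
| Suicidality, mixed model (13.4.1) | Without ratings, contributes nothing. Not diluted. |
| Suicidality, low-variability fallback (13.4.1) | Diluted if patients without ratings are kept in the denominator. The plan does not say. |
| Patients with an adverse event, and discontinuations for adverse events (10.12) | Diluted when expressed per randomised patient. |
| Creatine kinase (13.4.3) | Needs a Day 8 value. A patient never admitted is missing, not normal. |
| POSS (13.4.2) | A repeated score on dose days. Not a proportion. |
| Vital signs (13.8) | Post-dose windows only. |
| Achiness, anxiety, insomnia (13.5) | Repeated scores. Not proportions. |

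**Formula.** Let p be the risk in dosed patients, u the risk in never-dosed patients and q the share never dosed. The risk in all randomised is (1 − q)p + qu. For edema discontinuation u = 0, so the risk is (1 − q)p. If q is equal in both arms, the risk difference is also multiplied by 1 − q. For adverse events u may be above zero, because 15.2 starts reporting at screening; the factor 1 − q is then the extreme case.

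**Inputs.** Arm sizes come from section 3.0: "60 randomized to PGB/LFX; 30 to PGB-PLA/LFX". The value of q is not given. I assume 5%, 10% and 20%, that is 3, 6 and 12 of the 60 pregabalin patients.

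**Absolute risk, pregabalin arm (illustrative event counts)**

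| Events | Of 60 randomised | Of 57 dosed | Of 54 dosed | Of 48 dosed |
|---|---|---|---|---|
| 3 | 5.00% | 5.26% | 5.56% | 6.25% |
| 6 | 10.0% | 10.5% | 11.1% | 12.5% |

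**The planned comparison is an odds ratio from logistic regression.** Assumed risks in dosed patients: 12% versus 2%.

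| Never dosed (pregabalin / placebo) | Risks | Difference, points | Odds ratio |
|---|---|---|---|
| 0 / 0 | 12.0% v 2.0% | 10.0 | 6.68 |
| 10% / 10% | 10.8% v 1.8% | 9.0 | 6.61 |
| 20% / 20% | 9.6% v 1.6% | 8.0 | 6.53 |
| 10% / 0 | 10.8% v 2.0% | 8.8 | 5.93 |
| 0 / 10% | 12.0% v 1.8% | 10.2 | 7.44 |

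For example, at 10% in both arms: (0.108/0.892) ÷ (0.018/0.982) = 6.61.

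**Scale for edema itself.** Section 7.3.8 cites withdrawal for peripheral edema in about 1% of pregabalin patients with diabetic neuropathy. At that rate 60 × 0.01 = 0.6 events are expected, and the chance of none is 0.99^60, about 55%. With q = 10% the 1.0% becomes 0.9%.

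**The case against.** The strongest reply is that few or no patients may go undosed. Nowhere does the protocol say that it expects any. Section 9.1.2 lets COWS and SOWS be repeated until the dosing criteria are met. The pulse and blood-pressure rules in 7.3.3 hold a dose and do not by themselves end treatment, and 10.2 already excludes a pulse below 50 at screening. Under 7.3.3.1 a missed noon dose on Day 1 moves to the 16:00 slot. If randomisation takes place at admission, the group shrinks further. All of this stands, and it is why q is an assumption with zero as a possible value. It does not close the gap: two sections randomise before admission, and the ECG and COVID checks remain even if randomisation is at admission.

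A second reply is that counting such patients as event-free is an inference, because the plan has no missing-data rule for safety. That stands for the suicidality fallback: a patient admitted but undosed would have real daily C-SSRS ratings, and one never admitted would have none. It does not stand for edema discontinuation, where the answer for an undosed patient is known.

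A reader might infer more than this in three ways, none supported by the documents:

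- *That upper confidence limits are understated.* None are planned; 13.4 and 13.8 specify models and Wilcoxon tests. If one were added for zero events, the exact two-sided 95% limit, 1 − 0.025^(1/n), would be 5.96% on 60 and 6.60% on 54.
- *That all the proportion-based safety outcomes are diluted.* Creatine kinase needs a measured Day 8 value, and suicidality is a proportion only in its fallback.
- *That the pregabalin dizziness rates in Table 4 show the size.* Dizziness is not an outcome in 13.4 or 13.5. Those rates come from placebo-controlled neuropathy trials, whereas both arms here receive lofexidine, which itself commonly causes dizziness (7.4.3).

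**Conclusion.** The point holds in limited form. Followed as written, 13.6 puts never-dosed patients into the edema-discontinuation proportion as non-events. It does the same in the suicidality fallback if unrated patients are kept, and in the 10.12 adverse-event counts once these are expressed per patient. Absolute risks and, under equal non-dosing, risk differences are then multiplied by 1 − q, a relative loss of 5% to 20% over the assumed range and none at q = 0. For adverse events that is the largest loss, since undosed patients may report some.

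The between-arm odds ratio is nearly unchanged if non-dosing is equal across arms, which blinding before the first dose makes likely on average. With 60 and 30 patients, chance imbalance can move it in either direction. It would be wrong to conclude that the arm comparison is biased toward safety in general.

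The size in this trial cannot be known from the documents. The 40% dropout in 13.2 is an overall rate and says nothing about patients never dosed. At the cited 1% edema withdrawal rate the practical effect on that outcome is small. This is a worthwhile correction and not a threat to the trial's conclusions.

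**What to change.** Reword 13.6 to name two sets:

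- **Efficacy (13.3) and the SOWS- and ISI-based outcomes in 13.5:** all randomised subjects, as randomised. Achiness and anxiety are items of the primary scale, so they should share its population.
- **Safety (13.4, 13.8 and adverse events):** randomised subjects who received at least one dose of study medication, by treatment received.

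Report the number never dosed by arm. State for the suicidality fallback whether patients without ratings are in the denominator. Reconcile sections 3.0, 9.0, 9.1.1, 9.1.2 and 10.0 on when randomisation occurs.

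The cost is a sentence or two in the plan and a slightly smaller safety set. Because non-dosing is settled before any drug is taken and under the blind, leaving these patients out should not bias the safety comparison.

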13.7 ADVERSE EVENT RECORDING AND REDCAP SYSTEM ENTRY

AE names will be recorded based on the Medical Dictionary for Regulatory Activities (MedDRA) preferred terms found in the REDCap Database. Information regarding adverse events (AEs) will be recorded in REDCap and on an adverse event log and will include the following:

- AE Description
- AE Code
- Expectedness
- Date of Onset/ Change in Severity
- Continuous or Intermittent
- Severity
- Seriousness
- Study Drug Relatedness
- Action Taken Regarding Study Drug
- Other Actions Taken
- Outcome

Coding will be from a list of terms provided to each site formulated using MedDRA medical terminology.

13.8 VITAL SIGNS

Vital sign data (HR and BP) will be presented as summary statistics of maximum (max) absolute values, max change from baseline, and time to max value during the 1-hour period after each dose of study medication. Data will be compared between groups and within groups by study day by Wilcoxon rank sum statistic. Effects will be considered statistically significant at a two-sided p < 0.05.

